13.4.1 Adverse Event Reporting to IRB

Adverse events and SAEs will be reported to the IRB of record per local IRB policy.

13.4.2 Adverse Event Reporting to the DSMB

Adverse events and SAEs will be reported to the DSMB of record per local policy. The UFHCC DISC will be notified of serious adverse events within 5 business days of Coordinating Center notification.

13.4.3 Adverse Event Reporting to the FDA

Safety reporting will be in accordance with FDA requirements. It is the responsibility of the IND sponsor to report to the FDA in accordance with 21 CFR 312.32 as follows:

- Report any unexpected fatal or life-threatening suspected adverse reactions associated with use of the drug by telephone or fax as soon as possible but no later than **7 calendar days** after initial receipt of the information.
- Report any serious and unexpected suspected adverse reactions if there is evidence to suggest a causal relationship between the drug and the adverse event, as well as results from animal studies that suggest significant clinical risk within **15 calendar days** after receipt of this information.

A summary of Grade II (related) and Grade III toxicities, all IND safety reports and subject deaths during participation in the investigation will be submitted by the sponsor with the IND annual report.

13.4.4 Adverse Event Reporting to Sites

The Coordinating Center will notify site PIs of any adverse events associated with the use of the investigational vaccine that is both serious and unexpected within **15 calendar days** of the notification of the event. These reports should be submitted to the IRB of record in accordance with local policy. Any changes to the protocol and/or consent will be initiated by the Coordinating Center and distributed to participating sites for review by the IRB.

13.5 Potential Risks

13.5.1 Allergic Reactions to DC Immunization

Injection of antigen presenting cells may result in an allergic reaction, which could include redness and swelling at the injection site, itching, hives, low blood pressure, difficulty breathing, or in the most extreme circumstances, death. In addition, if the immune system becomes overly activated, potential discomforts may include pain, redness and swelling at the injection site.

13.5.2 Cerebral Edema

Cerebral edema may be secondary to the disease process itself, the surgical procedure, necrosis from previous radiation, or inflammation due to immune infiltration of the brain or destruction of tumor cells. Symptoms may include, but are not limited to, severe headache, confusion, lethargy, unresponsiveness, coma, or focal neurological deficits. Patients will be monitored throughout the course of the study and those patients with any signs or symptoms of cerebral edema may need their steroid doses increased, treatment with an osmotic diuretic, or surgical decompression. Edema that fails to respond to aggressive therapy may lead to permanent neurological impairment. The probability of this risk can be predicted to some degree based upon tumor size, location, pre-operative neurological impairment, and post-operative course prior to DC injections. Patients will be monitored throughout the course of the study.

13.5.3 Infection

The DC or PBMC injections may include the risk of infection due to potential contamination in the laboratory. This may result in localized redness, swelling, or induration at the injection site. In the most extreme situation, this may lead to systemic bacterial/fungal sepsis and possibly death. The probability of this risk is relatively low, given the small injection volume and the fact that the DCs and PBMCs will be strictly tested for sterility. The risk of infection due to potential contamination of the DCs and PBMCs in the laboratory will be minimized by biosafety quality assurance and testing. All cell cultures will be handled in a core tissue culture facility dedicated to the processing of human cells. Following injections, patients will be monitored throughout the course of the study for any signs and symptoms of infection. If an active infection is suspected, patients will be cultured and treated with appropriate antibiotics.

13.5.4 Delayed Autoimmune Diseases

It is possible that delayed autoimmune disease(s) may develop as a result of injection with DCs or PBMCs. This means that the immune system may be stimulated to attack natural tissue in the body. Animal studies have reported the development of autoimmunity in the context of vaccination and recovery from lymphopenia. However, our current experience with DC and PBMC vaccination in glioma patients has not demonstrated evidence of autoimmunity in treated patients. It therefore, is unknown what the risk of delayed autoimmune disease is for this study.

13.5.5 Phlebotomy

Drawing blood or inserting an intravenous catheter into an arm vein may result in bruising or swelling in the area of the insertion, bleeding at the site of the needle puncture, light headedness, fainting and very rarely, local infection, which may be severe.

13.5.6 Leukapheresis

As with any donation of blood, a variety of minor reactions may occur with leukapheresis, which include fainting, dizziness, or nausea. Uncommon but serious complications may also result, which include bleeding, infection, an adverse reaction to the anticoagulant or replacement fluids, hypocalcemia, hypotension, shock, convulsions, air emboli, heart failure, or the inability to transfuse blood back into the patient. These risks are reduced by the fact that the procedure will be performed by qualified staff at a specialized clinical hemapheresis unit. Patients will be carefully monitored throughout the procedure by trained nursing and medical staff. Calcium gluconate (2 mg PO) may be given to minimize the risks of hypocalcemia, fluid supplementation may be given to minimize hypotension, and blood will be routinely screened for infectious disease in accordance with institutional practices to minimize the risk of transmitting infection.

13.5.7 Central Venous Catheter

Some patient may require placement of a dialysis-type central venous catheter for the leukapheresis procedure. Separate operative/procedural consent will be obtained from the surgeon/proceduralist placing the central line. The surgeon/proceduralist may use fluoroscopy to place the central venous catheter and ensure that it is in a satisfactory position. Fluoroscopy involves low dose radiation and is low risk. Risk of central line placement include (but not limited to): bruising, bleeding, injury to the vessel which may be permanent, possible injury to adjacent structures/organs, pneumothorax, infection and postoperative pain/discomfort. Removal of the central line is low risk but does include possible thrombosis or stenosis of the vessel. This may prevent future use of this vessel for additional leukapheresis.

13.5.8 MRI

The risks and/or discomforts associated with the performance of MRI include the anxiety produced from being in a tight, enclosed space (claustrophobia). In addition, the machine operates using a large and powerful magnet. The magnetism of the machine attracts certain metals: therefore, people with these metals in their bodies (specifically pacemakers, infusion pumps, metal aneurysm clips, metal prostheses, joints, rods or plates) will be imaged by CT scan. Patients will also be checked to make sure that they do not bring any metal objects into the MRI facility. Dental fillings are less affected by the magnetic fields generated and are therefore permitted. It will be asked that patients let the physicians conducting this study know of any metal in their bodies other than dental fillings.

13.5.9 GM-CSF

Injection of GM-CSF may increase the risk of infection, lower platelets, or cause fluid retention. GM-CSF also may result in an allergic reaction, which could include redness and swelling at the injection site, itching, hives, flushing, syncope, low blood pressure, difficulty breathing, or in the most extreme circumstances, death. In addition, if the immune system becomes overly activated, potential discomforts may include pain, redness and swelling at the injection site.

13.5.10 Td

The following adverse events have been identified during post-approval use of MassBiologics' Td. Because these reactions are reported voluntarily from a population of uncertain size, it is not always possible to reliably estimate their frequencies or to establish a causal relationship to vaccination. The following adverse events were included because of seriousness or frequency of reporting: injection site reactions, including pain, tenderness, erythema, induration, pruritis,

swelling and warmth; peripheral edema, pyrexia, malaise; dizziness, headache, convulsions, myalgia, musculoskeletal stiffness or pain, arthralgia; rash; nausea; and cellulitis.

13.5.11 Allergic Reactions to Contrast Agents

During the MRI, patients will be given a contrast agent. The agent is given routinely to obtain enhanced MRI scans of the brain. The agent is administered through the vein and requires the placement of an IV catheter. The catheter placement is similar to drawing blood except that the catheter remains in the vein during the time the agent is actively delivered. The risks of a blood draw and insertion of a catheter are similar. There have been a few, rare cases of allergies to the agent used in MRI contrast enhanced scans. Patients with any known severe allergies to contrast agents will be excluded from the study. Patients with mild allergies (i.e., rash only) will be pretreated with Tylenol and Benadryl prior to injection of the contrast agent.

13.5.12 Temozolomide

TMZ has been well tolerated by both adults and children with the most common toxicity being mild myelosuppression. Other, less likely, potential toxicities include nausea and vomiting, constipation, headache, alopecia, rash, burning sensation of skin, esophagitis, pain, diarrhea, lethargy, hepatotoxicity, anorexia, fatigue and hyperglycemia. Hypersensitivity reactions have not yet been noted with TMZ. As in the case with many anti-cancer drugs, TMZ may be carcinogenic. Rats given TMZ have developed breast cancer. The significance of this finding for human is not presently known. TMZ therapy will be followed but given as standard of care. If toxicities occur, the Principal Investigator and primary physician will titrate therapy based on standard clinical guidelines.

13.5.13 Confidentiality

Participation in research may result in a loss of privacy if confidentiality is breached. Only designated members of the study team will have access to individually identifiable private information. Data collected from clinical records or patients will be recorded in OnCORE that uses Gatorlink authentication. Clinical records containing PHI will be maintained as source documentation and stored in secure, limited access, locked offices. Records will be made available to individuals involved with the study, the clinical staff administering the study, and regulatory representatives such as the IRB, FDA, OHRP and funding agency. Any publications resulting from this study will not include patient identifying data.

14 QUALITY CONTROL AND QUALITY ASSURANCE

14.1 Data and Safety Monitoring Plan

14.1.1 Data Monitoring Plan

Adverse events meeting the definition of an SAE and any grade 2 or greater AEs where there is a possible, probable or definite relationship between the AE and investigational drug must be reported to the Coordinating Center within 24 hours of the investigator's discovery. These will be assessed by the Protocol Chair and reported to the IRB, DSMB, FDA and other participating investigators as outlined in the protocol.

The UFHCC SRMC conducts initial review of IITs and determines the level of risk which corresponds with DISC review requirements. The UFHCC DISC will conduct monitoring and audit activities as outlined in the DISC Charter. The results of such activities will be provided to the PI, IND sponsor and IRB.

The UF study team will conduct annual QA self-assessments that include review of regulatory documentation (e.g., IRB documentation, FDA IND records, IND Sponsor-Investigator responsibilities), recruitment procedures, informed consent process/form documentation, subject selection, AE and SAE reporting, CRF and source documents.

The Coordinating Center will periodically review data entry and source documents uploaded into OnCore or other electronic source, and notify sites of missing, incomplete or inconsistent data as applicable.

Orlando Health Cancer Institute site data will be monitored by the coordinating center lead coordinator and regulatory manager by reviewing source documents uploaded in the study database (UF OnCore).

Duke will manufacture their own IP under their own IND and will perform site-specific monitoring that will be reported to the Coordinating Center/Protocol Chair as described in the protocol.

14.1.2 Data Safety Monitoring Board

Oversight and monitoring of study related activities such as the safety of research participants, appropriateness of the study, and integrity of the data, will be provided by the University of Florida Health Cancer Center DSMB, now called the Data Integrity and Safety Committee (UFHCC DISC), in accordance with established policies, procedures and timeframes. DISC reports and correspondence will be provided to participating investigators for review and submission to local oversight committees as required.. All reports generated by Duke pertaining to study conduct, will be sent to the University of Florida PI and Protocol Chair. DSMB reports should be submitted to the IRB per local policy.

14.2 Audits

An IRB or other local oversight group may conduct audits to evaluate compliance with the protocol and the principles of GCP. The PI will provide the auditor(s) with direct access to all relevant documents and to allocate his/her time and the time of the study team to the auditor(s) in order to discuss findings and any relevant issues.

Audits are designed to protect the rights and well-being of human research subjects. Audits may be routine or directed (for cause). Routine audits are selected based upon risk metrics generally geared towards high subject enrollment, studies with limited oversight or monitoring, Investigator initiated Investigational Drugs or Devices, federally-funded studies, high degree of risk (based upon adverse events, type of study, or vulnerable populations), Phase I studies, or studies that involve Medicare populations. Directed audits occur at the directive of the IRB or an authorized Institutional Official.

Audits examine research studies/clinical trials methodology, processes and systems to assess whether the research is conducted according to the protocol approved by the IRB. The primary purpose of the audit/review is to verify that the standards for safety of human subjects in clinical trials and the quality of data produced by the clinical trial research are met. The audit/review will serve as a quality assurance measure, internal to the institution. Additional goals of such audits are to detect both random and systemic errors occurring during the conduct of clinical research and to emphasize “best practices” in the research/clinical trials environment.

Duke University and the University of Florida have an auditing mechanism in place and each institution will be responsible for auditing their respective data. Additionally, Duke University will send copies of all audit findings to the University of Florida who, based on these findings, can request additional documentation or conduct an on-site visit.

14.3 Data Management and Processing

14.3.1 Study Documentation

Study documentation includes but is not limited to source documents, case report forms, screening/enrollment, delegation of authority and monitoring logs (as applicable), appointment schedules, correspondence with sponsors or regulatory bodies/committees, and regulatory documents that can be found in the “Regulatory Binder” (electronic or hard copy), which includes but is not limited to signed protocol, amendments, and investigator’s brochure (as applicable), approved and signed informed consent forms, IRB submission documents, approvals and correspondence, CVs for investigators and sub-investigators, FDA Form 1572, financial disclosure forms, laboratory certifications and reference ranges, and clinical supplies receipts and distribution records.

Source documents are original records that contain source data, which is all information in original records of clinical findings, observations, or other activities in a clinical trial necessary for the reconstruction and evaluation of the trial. Source documents include but are not limited to hospital records, clinical and office charts, laboratory notes, memoranda, subjects’ diaries or evaluation checklists, pharmacy dispensing records, recorded data from automated instruments, copies or transcriptions certified after verification as being accurate copies, microfiches, photographic negatives, microfilm or magnetic media, x-rays, subject files, and records kept at the pharmacy, at the laboratories and at medico-technical departments involved in the clinical trial. When possible, the original record should be retained as the source document. However, a photocopy is acceptable provided that it is a clear, legible, and an exact duplication of the original document.

14.3.2 Site Activation

A site is considered activated when the site has received official written documentation from the Protocol Coordinating Center that the site has been approved to begin enrollment. At a minimum, each participating clinical site must have the following documentation on file at UF prior to study activation:

- IRB approval of the study in the form of a letter or other official document from the participating institution’s IRB of record. This documentation must show the version of the protocol approved by the IRB.
- IRB approval of an informed consent form. The consent must include a statement that data will be shared with UF, including the UFHCC, the DSMB (if applicable), and the

UF study team.

- Protocol signature page signed and dated by the investigator at each participating site.

The applicable IND sponsor is responsible for obtaining and maintaining signed and dated FDA Form 1572, and the CVs, applicable licenses and FDFs of all investigators listed on the 1572.

The Coordinating Center is responsible for disseminating study updates, protocol and/or investigator brochure amendments, reportable adverse events, and informed consent modifications to all participating sites. Protocol/consent modifications and IB updates will be forwarded electronically to participating sites within 4 weeks of UF IRB approval. Activated participating sites are expected to submit protocol/consent/IB modifications to their local IRBs within 4 weeks of receipt unless otherwise noted. Documentation of IRB approval should be provided to the Coordinating Center within 2 weeks of receipt of approval. The Coordinating Center should review all revised consent forms prior to submission to the IRB.

Documentation of participating sites' IRB approval of annual continuing reviews, protocol amendments or revisions, SAE reports, and any protocol violations/deviations/exceptions must be on file at UF.

The investigator or a designee from each institution must participate in conference calls, as scheduled, to update and provide information regarding the progress of the trial.

14.3.3 Case Report Forms

Electronic case report forms (eCRFs) will be utilized for this trial. Only the PI and key study personnel listed on the study delegation log are permitted to make entries, changes, or corrections in the case report forms. Source documents that support data entry should be available for monitoring or audit. The Coordinating Center will periodically review data entry and notify sites of missing, incomplete or inconsistent data.

14.3.4 Data Management Procedures and Data Verification

Users of the electronic CRF will have access based on their delegated specific roles on the study. Completeness of entered data will be checked and cross-referenced to verify accuracy. Missing or implausible data will be highlighted for the PI requiring appropriate responses (i.e. confirmation of data, correction of data, completion or confirmation that data is not available, etc.).

The database will be reviewed and discussed prior to database closure, and will be closed only after resolution of all remaining queries. An audit trail will be kept of all subsequent changes to the data.

15 STATISTICAL METHODS AND DATA ANALYSIS

15.1 Study Design Overview

The primary goal of this randomized phase II study is to determine whether the addition of pp65-LAMP mRNA DC vaccination in adult patients with newly-diagnosed GBM receiving dose-intensified TMZ will be a treatment worthy of investigation in a large phase III study. A secondary

objective will be examination of the immunologic responses induced by full-length vs short LAMP sequences.

Although this randomized phase II study is comparative, it will not be definitive as the assessment will be conducted with a large false-positive rate. We have included a concurrently followed control arm in the trial design in lieu of a historical control group to ensure that appropriate comparisons can be made without concern that the patients receiving standard treatment differ in prognostic factors or standards of care (Rubinstein, 2009; Ratain and Sargent, 2009; Rubinstein et al., 2005).

We will randomize eligible patients, after enrollment, to one of 3 study arms in which they will receive 21-day TMZ concurrently with one of the following treatments:

Arm #	Vaccine	Skin Preparation
1	pp65-shLAMP mRNA DCs with GM-CSF	Tetanus
2	pp65-fLAMP mRNA DCs with GM-CSF	Tetanus
3	PBMCs	Saline

Randomization will be stratified by:

- Age 69 years old and younger; or 70 years old and older
- RPA Class (III, IV, or V)
- CMV seronegative or seropositive

We will use a permuted block randomization scheme with a 1:1:1 study arm allocation ratio and a block size of 6 within each stratum.

Adapted RPA Stages For Malignant Gliomas (Survival With Concurrent Temozolomide and Radiation Therapy vs Radiation Therapy alone)				
Stage	Characteristics	Median OS	2-year OS	p-value vs. control
III	Age <50, PS 0	21 vs. 15 mo	43% vs. 20%	p<0.0001
IV	Age <50, PS 1-2 Age >=50, Surgery, MMSE >=27	16 vs. 13 mo	28% vs. 11%	p<0.01
V	Age >=50 and either Biopsy only or MMSE <27	10 vs. 9 mo	17% vs. 6%	p=0.05

Approximately 200 patients will be enrolled in the study, randomized and receive “standard-of-care” radiotherapy concurrent with TMZ under the assumption that approximately 120 patients will be vaccinated according to treatment arm.

A Data Sharing Agreement has been established with Immunomic Therapeutics, Inc. and the University of Florida. A Limited Data Set will be sent to evaluate immunogenicity and clinical efficacy of the vaccine products used within this clinical trial (for patients treated at the UF site

only) in which Immunomic Therapeutics, Inc. has scientific and potential commercial interest. Data will be provided within 6 months of study completion. Applicable patient identifiers will be removed before sending the limited data set. A separate data sharing agreement may be established by Immunomic Therapeutics, Inc. with Duke University.

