9 INVESTIGATIONAL PLAN

9.1 Overview

The eligibility criteria for this trial will be similar to those used in the RTOG 0525 study (Aldape 2009). Prior to the initiation of TMZ and external beam RT, patients will sign consent and undergo leukapheresis for PBMCs in accordance with **SOP-UFBTIP-131**.

Up to 200 newly diagnosed WHO Grade IV glioma patients will be enrolled in the study. Eligible patients will be randomized, undergo leukapheresis and receive “standard-of-care” radiotherapy concurrent with TMZ under the assumption that approximately 120 patients will be vaccinated according to treatment arm in this placebo controlled, single blinded, randomized Phase II study.

Prior to leukapheresis, patients will be randomized to receive one of three treatment regimens with dose-intensified TMZ treatment at 100 mg/m²/day for 21 days with an allocation ratio of 1:1:1 into one of three arms to receive:

- 1) pp65-shLAMP mRNA DCs with GM-CSF 150 µg (Td skin prep)
- 2) pp65-fLAMP mRNA DCs with GM-CSF 150 µg (Td skin prep)
- 3) Unpulsed PBMCs (saline skin prep)

Randomization will be stratified by;

- Age 69 years old and younger, who will receive dose-intensified adjuvant temozolomide; or 70 years old and older who will receive standard dose adjuvant temozolomide.
- Recursive Partitioning Analysis (RPA) class (III, IV, or V). To determine RPA class, Performance Status (PS) will be determined from KPS conversion using the ECOG comparison scale for patients ≤ 50 years; a Mini-Mental State Examination will be performed at enrollment for patients ≥ 50 years.
- CMV seronegative or seropositive

Within 7 weeks of surgery, patients will undergo standard RT with concurrent TMZ at a target dose of 75 mg/m²/day.

Patients will receive the initial cycle of TMZ 4 (+/- 1) weeks after completing RT. Study drugs will be given intradermally at day 22-24 after the first TMZ cycle and divided equally between both inguinal regions in accordance with **SOP-UFBTIP-128**. All patients will receive Td booster (5 Lf) with vaccine #1 regardless of booster history. Vaccine #2 and #3 will occur at 2 week intervals.

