9.2 Registration Procedures

To register a patient to this study, patient demographic data will be entered into the UFHCC OnCore database by the participating site coordinator after subject consent has been obtained and documented. The Oncore database will assign a study ID to the patient after eligibility is confirmed and an “On Study” Date is entered in Oncore. Patients who signed consent but are deemed not eligible to participate, will be assigned a failed-screening ID by the Coordinating Center Project Coordinator.

For patients enrolled at an outside participating site who will receive study treatment at the University of Florida, the ATTAC Registration Form will be submitted to the Protocol Coordinating Center along with applicable supporting documentation. Once the patient has been entered in the UFHCC database and the registration form has been received, the Protocol Coordinating Center will confirm eligibility and randomize eligible patients. The patient’s assigned study ID will be forwarded to the participating site coordinator by email.

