9.3 Randomization Procedures

Patients will be randomized by the designated site personnel where study treatment will be administered in accordance with SOP-UFBTIP-140.01.

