15.2 Sample Size Justification for Vaccine Comparison

The primary focus of this trial will be to assess the worthiness of pp65-LAMP mRNA DC vaccine for further investigation by comparing overall survival (OS) between the active treatment group (Arms 1 and 2 combined) and the control group (Arm 3). Because this test for efficacy will be made within the framework of a phase II trial, we have constrained sample size requirements to yield adequate power to detect a clinically relevant improvement in OS at the expense of the false positive rate (α -level or Type I error rate). Adopting guidelines proposed by Ratain and Sargent (2009) and Rubinstein et al (2005), our proposed sample size of $40 + 40 = 80$ patients in the treatment group and 40 patients in the control group will allow detection of a clinically relevant improvement in the median OS time of the treatment group with 90% power at a one-sided α -level of 0.2.

In determining the effect size that can be detected by our proposed sample size, we considered using as a control reference level the median OS estimate of 14.6 months (95% CI: 13.2 to 16.8) reported by Stupp et al (2005) for patients receiving radiotherapy plus TMZ (RT+TMZ) for newly-diagnosed GBM (40% of patients in the Stupp trial were grossly resected). In the Stupp trial, randomization occurred prior to any post-surgical treatment, and the timing of randomization in our study will be similar. However, in our study, patients will not begin to experience potential differential effects due to treatment until after their first vaccination, which will occur approximately 15 weeks after randomization. To determine an appropriate control reference level for median OS for an index day 15 weeks after randomization, we carefully transferred the coordinates of multiple points along the Stupp RT+TMZ OS curve into a statistical software package. We determined that median OS relative to a starting time 15 weeks after the Stupp index day would be 13.8 months. We also observed that RT+TMZ OS times appeared to approximately follow a Weibull distribution with a shape parameter = 1.20, indicating a slightly accelerating baseline hazard function. Upon examining in a similar manner the RT+TMZ OS curve reported in the paper by Gilbert et al (2013), we also observed approximately Weibull-distributed OS times with shape parameter = 1.16.

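### A fixed, printed block size of 6 with site-run, single-blind randomization makes up to about a quarter of DC-versus-control assignments deducible, mainly between consent and randomization

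*Combined protocol and SAP*

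**What the plan says.** Section 15.1 sets out a "permuted block randomization scheme with a 1:1:1 study arm allocation ratio and a block size of 6 within each stratum". The strata are formed by age (69 or younger, 70 or older), RPA class (III, IV, V) and CMV serostatus; site is not listed as a factor. The size is constant and is printed in the protocol.

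Section 9.3 states: "Patients will be randomized by the designated site personnel where study treatment will be administered", under an SOP that is not part of the documents. Section 9.2 makes an exception for patients enrolled at an outside site but treated at the University of Florida: for them, "the Protocol Coordinating Center will confirm eligibility and randomize eligible patients".

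Section 9.1 describes a "placebo controlled, single blinded, randomized Phase II study" without saying who is blinded. Staff who prepare or give treatment can tell the arms apart: DC vaccines contain GM-CSF and PBMC vaccines only saline (9.6.3), and skin pretreatment is Td or saline by arm (9.7).

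Randomization follows enrolment (15.1) and precedes the first leukapheresis (10.2). Nothing in the documents describes varying block sizes, withholding the size from sites, or keeping past assignments from those who enrol patients.

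**The concern.** At 1:1:1, each block of 6 holds two patients per arm. Because the primary comparison pools Arms 1 and 2 against Arm 3 (15.2), that means 4 DC slots and 2 control slots. Someone who knows the block size and the assignments already made can tell when every remaining slot in the block must be of one kind. Concealing the next list entry does not prevent this, because the deduction uses past entries only.

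If the next assignment can be deduced before a patient is committed, eligibility judgements or timing can be influenced by it. Several entry criteria leave room for judgement, such as recovery from surgery (8.1) and the exclusions left to the investigator's opinion (8.2). Prognosis could then differ between arms within strata. The stratified Cox analysis in 15.3.1 uses only age, RPA class and CMV status, so it would not remove such a difference. Section 15.1 justifies the concurrent control arm as protection against prognostic differences, and deducible allocation weakens that protection.

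**Working it through.** **The plan's own figure.** The plan gives no predictability figure. Its design figure, 77 deaths for a hazard ratio of 0.60 at 90% power, one-sided 0.20 and 80:40 allocation (15.2), is confirmed as context: (0.8416 + 1.2816)² / [(2/3)(1/3)(ln 0.6)²] = 77.7, and power at 77 deaths is 0.898. It is not in dispute.

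**Inputs from the documents.** Block of 6 with 4 DC and 2 control; about 200 randomized (15.1). Strata: 2 × 3 × 2 = 12. RPA class III requires age under 50 (table in 15.1), so the two strata combining it with age 70 or over stay empty, leaving 10.

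**Full blocks, all earlier assignments known.** With k slots left, the next one is certain when all k are of one kind, with probability [C(4,k) + C(2,k)] / C(6,k):

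- k = 1 (6th slot): 6/6 = 1
- k = 2 (5th slot): 7/15
- k = 3 (4th slot): 4/20 = 1/5
- k = 4 (3rd slot): 1/15
- 1st and 2nd slots: 0

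The sum is 26/15 certain slots per block, and (26/15)/6 = 13/45 = 28.9%. Of all slots, 22.2% are known to be DC and 6.7% known to be control. The exact arm (1, 2 or 3) is certain for 20%.

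**Departures from full knowledge.** The first three rows below count unfinished last blocks by simulating 200 patients. Stratum shares are assumptions (20% aged 70 or over; RPA III/IV/V 15/65/20%; 40% CMV-positive; site splits 70/30 or 50/30/20); equal strata gave nearly the same results for one and two lists. The shared-list rows use full blocks and grant that staff know where each block begins.

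| Situation | DC versus control certain |
|---|---|
| One list per stratum, all assignments seen | 26% (0.26 × 200 = 52 patients) |
| Separate lists at two sites | 23.5% (0.235 × 200 = 47 patients) |
| Separate lists at three sites | 21% |
| Shared list, 80% of assignments seen | 17% |
| Shared list, 70% seen | 12% |
| Shared list, 50% seen | 6% |
| All assignments seen, CMV serostatus not yet known | about 5% |

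The last row is low because, without serostatus, the next slot in both candidate CMV strata must be certain and the two must agree.

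**Alternative schemes.** These are the certain shares for an observer who knows the set of sizes and every past assignment. Random sizes 6 and 9 give about 5.5%; 3, 6 and 9 give 3.8%; 3 and 6 give 9.8%. A larger fixed block helps much less: 9 gives 21.4% and 12 gives 17.0%.

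**The case against.** The strongest reply is that the sequence of steps limits what anyone can foresee. CMV serology, and the MMSE that separates RPA IV from V in resected patients aged 50 or over, are listed with consent among the enrolment procedures (10.1), and randomization comes afterwards. A reader might infer that recruiters know the arm while deciding whom to approach. The documents do not support this: before serostatus is known the certain share is only about 5%. Footnote 22 of section 10.7 accepts infectious-disease results from within 30 days of enrolment, so serostatus may sometimes be known sooner, but nothing says this is routine. This objection stands and moves the exposure to the interval between consent and randomization.

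A reader might also infer that the true false-positive rate is well above 0.20. Illustrative log-rank calculations with no treatment effect, an unmeasured factor with hazard ratio 2 and 50% prevalence, and every certain slot steered by 10, 20 or 30 percentage points give about 0.25, 0.29 and 0.35 under full-block knowledge. With about 12% of slots certain they give about 0.22, 0.23 and 0.27; with 5-6%, about 0.21, 0.23 and 0.23. The factor, its strength and the steering all come from outside the documents, so none of these is an estimate for this trial.

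Three further points stand in part:

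- The randomization SOP is not available. The documents do not say that those who randomize also recruit, whether lists are per site, or who sees past assignments.
- OnCore assigns a study ID only after eligibility is confirmed (9.2). Accrual was slow (132 patients in more than four years, per the December 2020 entry in the change log), and chemoradiation must start within 7 weeks of surgery, so holding a patient back for a slot would seldom be practical.
- MGMT status is collected for analysis (10.1), residual enhancing disease may serve as a covariate (11.1), and patients with gross total resection are examined separately (15.3.1). Some of the relevant prognosis is therefore measured, although the stratified Cox analysis does not include it.

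None of this supplies a reason to keep the block size fixed and printed.

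**Conclusion.** The point holds in limited form. Fixed blocks of 6, stated in the protocol and run by site personnel in a single-blind trial, permit deduction of DC versus control for at most 28.9% of slots in full blocks, and for about 23-26% of 200 patients with one list per stratum or two site lists. Those figures require knowledge of the patient's stratum and of every earlier assignment in it. Under partial visibility or unknown serostatus the range is about 5-17%. The documents do not settle which case applies, so the whole range of about 5-26% should be stated. They establish an opportunity, chiefly after consent and before randomization. They give no evidence that anyone used it and no basis for quantifying an effect on the 0.20 error rate. A better method is available at little cost.

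**What to change.** **Section 15.1.** Replace the fixed size of 6 with randomly varying block sizes in multiples of 3 (for example 6 and 9), known only to the statistician who generates the list. This is the change that prevents most deduction, taking certain slots to about 5-6%.

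**Section 9.3.** Have the Coordinating Center issue every allocation after eligibility is confirmed in OnCore, extending what 9.2 already does for outside-site patients treated at the University of Florida. State whether lists are shared or per site, and who can see past assignments.

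**Patients already randomized.** The documents do not say whether accrual has closed, and new lists cannot protect earlier assignments. Add a sensitivity analysis of OS adjusted for MGMT status, postoperative residual enhancing disease and KPS, all already collected. Compare these factors between deducible and non-deducible slots, separately for DC and control, because steering would push the two in opposite directions. Numbers will be small: even at the full-block rate, 0.067 × 200 is about 13 deducible control slots. A null comparison would therefore reassure only weakly, and adjustment covers measured factors only.

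**Cost.** Regenerated lists, short edits to 9.3 and 15.1, and one added analysis. Balance within small strata becomes slightly looser. No extra patients or visits are needed.
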